7. If female, a status of non-childbearing potential or use of an acceptable form of birth control per the following specific criteria:
  - a. Non-childbearing potential (e.g., physiologically incapable of becoming pregnant, i.e., permanently sterilized (status post hysterectomy, bilateral tubal ligation), or is post-menopausal with her last menses at least one year prior to screening); or
  - b. Childbearing potential, and meets the following criteria:
    - i. Childbearing potential, including women using any form of hormonal birth control, on hormone replacement therapy started prior to 12 months of amenorrhea, using an intrauterine device (IUD), having a monogamous relationship with a partner who has had a vasectomy, or is sexually abstinent.
    - ii. Negative urinary pregnancy test at screening, confirmed by a negative urinary pregnancy test at randomization prior to receiving study treatment.
    - iii. Willing and able to continuously use one of the following methods of birth control during the course of the study, defined as those which result in a low failure rate (i.e., less than 1% per year) when used consistently and correctly: implants, injectable or patch hormonal contraception, oral contraceptives, IUD, double-barrier contraception, sexual abstinence. The form of birth control will be documented at screening and baseline.
8. Body mass index between 18-35 kg/m^2.
9. Concurrent psychotherapy will be allowed if the type (e.g., supportive, cognitive behavioral, insight-oriented, et al.) and frequency (e.g., weekly or monthly) of the therapy has been stable for at least three months prior to screening and if the type and frequency of the therapy is expected to remain stable during the course of the subject's participation in the study.
10. Concurrent hypnotic therapy (e.g., with zolpidem, zaleplon, melatonin, benzodiazepines or trazodone) will be allowed if the therapy has been stable for at least 4 weeks prior to screening and if it is expected to remain stable during the course of the subject's participation in the study. Patients can also continue treatment with benzodiazepines used for anxiety if therapy has been stable for at least 4 weeks prior to screening and if it is expected to remain stable during the course of the subject's participation in the study.

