#### H.2.b. EXCLUSION CRITERIA

A potential participant will NOT be eligible for participation in this study if any of the following criteria are met:

1. Female of childbearing potential who is not willing to use one of the specified forms of birth control during the study.
2. Female that is pregnant or breastfeeding.
3. Female with a positive pregnancy test at screening or baseline.
4. History during the *current* MDE of failure to achieve satisfactory response (e.g., less than 50% improvement of depression symptoms) to >7 treatment courses of a therapeutic dose of an antidepressant therapy of at least 8 weeks duration, according to the MGH ATRQ, as confirmed by the remote, independent MGH CTNI rater.
5. Total MADRS score of <20 at the screen visit or the baseline visit, or as assessed by the remote, independent MGH CTNI rater and reported to the site.
6. Current diagnosis of a substance use disorder (abuse or dependence, as defined by DSM V-TR™), with the exception of nicotine dependence, at screening or within 6 months prior to screening.
7. Current Axis I disorder, diagnosed at screening with the use of the Structured Clinical Interview for DSM-5 AXIS I Disorders (SCID-5), that is the principal focus of treatment and MDD the secondary focus of treatment for the past 6 months or more.
8. History of bipolar disorder, schizophrenia or schizoaffective disorders, or any history of psychotic symptoms in the current or previous depressive episodes.
9. History of anorexia nervosa, bulimia nervosa, or eating disorder not otherwise specified, within 5 years of screening.
10. Any Axis I or Axis II Disorder, which at screening is clinically predominant to their MDD or has been predominant to their MDD at any time within 6 months prior to screening.
11. In the judgment of the investigator, the subject is considered at significant risk for suicidal behavior during the course of his/her participation in the study.
12. Has failed to respond to ECT during the current depressive episode.
13. Has received VNS at any time prior to screening.
14. Has dementia, delirium, amnestic, or any other cognitive disorder.
15. Has a clinically significant abnormality on the screening physical examination that might affect safety, study participation, or confound interpretation of study results according to the study clinician.
16. Participation in any clinical trial with an investigational drug or device within the past month or concurrent to study participation.

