**TABLE 2– OVERVIEW OF STUDY SCHEDULE**

Screen Visit	Screening Period	V1 / Baseline Visit	V2	V3	V4	V5	V6	V7	V8	V9	V10	V11
Day -28 to Day -7	Taper (opt.) 5 half-lives of excluded psychotropic drug(s)	Day 0	Day 1	Day 2	Day 5	Day 8	Day 11	Day 14	Day 17	Day 21	Day 23	Day 28
		Baseline Assess.	Assess.	Assess.	Assess.	Assess.	Assess.	Assess.	Assess.	Assess.	Assess.	Assess.
		Intranasal Ketamine Admin.	Assess.	Assess.	Intranasal Ketamine Admin.	Intranasal Ketamine Admin.	Intranasal Ketamine Admin.	Intranasal Ketamine Admin.	Assess.	Intranasal Ketamine Admin.	Assess.	Assess.
		Study Drug*	Study Drug*	Study Drug*	Study Drug*	Study Drug*	Study Drug*	Study Drug*	Study Drug*	Study Drug*	Study Drug*	Study Drug*

\*Brexipiprazole or Placebo

Subjects will be screened for eligibility as detailed above. Study participants will be consented prior to the administration of any procedure or wash-out. Following a washout period, under the close supervision and monitoring of the study clinicians, for patients on psychotropic drugs (with the exception of ongoing antidepressant therapy and of ongoing hypnotic therapy), baseline assessment, MGH CTNI remote interview, and re-confirmation that all criteria for entry into the study are met, eligible subjects will be randomly assigned to one of two arms: brexpiprazole plus intranasal ketamine (n=25) or placebo plus intranasal ketamine (n=25). The brexpiprazole dose will be titrated in the following manner: 0.5 mg/day during the first week, at the Visit 5/Day 8 visit, the dose will be increased to 1 mg/day, at Visit 7/Day 14 the dose will be increased to 2 mg/day, and at Visit 9/Day 21, the dose will be increased to 3 mg/day. If the dose escalation is not tolerated, patient can go back to previous dose (fixed-flexible dose escalation). As per Table 2, all subjects will be followed for 28 days to examine the efficacy and tolerability of brexpiprazole plus intranasal ketamine’s effects. The study assessments will be performed at Days 0, 1, 2, 5, 8, 11, 14, 17, 21, 23, and 28 to assess the safety and efficacy of brexpiprazole plus intranasal ketamine compared to placebo plus intranasal ketamine treatment therapy in depressed patients who have demonstrated an inadequate response

to at least 2 adequate antidepressant therapies (ADTs) during the current MDE. Intranasal ketamine (40 mg) will be administered after all the assessments are completed on Days 0, 5, 8, 11, 14, and 21.

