screening phase to allow proper wash-out at the baseline/randomization visit (e.g., at least 5 half-lives of the drug). The screening period (between the screen visit and baseline visit) can be extended to allow for a clinically appropriate tapering of such medications, again under the close supervision of the study physician, who will see them weekly during the taper phase and to ensure that the discontinuation of the excluded psychotropic medications occurs at least 5 half-lives prior to the baseline visit. The investigator will determine that patients meet eligibility criteria and will collect the demographic and medical data permitting full characterization of the patient.

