## 1.2. PROCEDURES

### 1.2.a. LABORATORY/DIAGNOSTIC PROCEDURES

Once the patient has signed the informed consent document, the urine pregnancy and toxicity test will be performed at screen and baseline visits. 12 lead ECGs will be measured at the screen visit and at visits 4,5,6,7 and 9 as required by the physiological monitoring procedures in the Manual of Operations . A Chemistry and CBC will also be obtained at the screening visit, and at Visits 7 and 11. If TSH is high, subject may be tested for T4 at the request of the PI. Weight, oral temperature, and seated and supine pulse and blood pressure (Vital Signs) will be recorded at each visit. Height is recorded at the Screening Visit only. (BMI is calculated automatically in the EDC). At the screen visit, Visit 7 and at Visit 11, patients will have a physical examination. The laboratory tests required are listed in Table 4, below. Laboratory tests will be performed at the site, and each site will provide their laboratory normal to the coordinating center.

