#### I.4.d. PREGNANCY

If a subject (or subject's partner) becomes pregnant during the study, it must be reported in within 24 business hours of the time the investigator becomes aware of the event and in accordance with the procedures described on the Pregnancy Report Form. Pregnancy in itself is not regarded as an AE unless there is a suspicion that a study drug may have interfered with the effectiveness of a contraceptive medication. Any pregnancy that occurs from Day 1 to 30 days following the last dose given will be followed for gestational outcome and the outcome would be reported to the Sponsor.

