#### I.5.b. PROTOCOL VIOLATIONS

##### I.5.b.1. PROCEDURE FOR NON-COMPLIANT PATIENTS

Patients will be scheduled for the period of study participation when they are available to come in for study visits. Patients who miss one visit will be allowed to make up that visit within a window that depends on the visit. Every effort will be made by the site to adhere to the study visit schedule, in order for assessments to be able to be performed at the stipulated time points. Patients who miss more than one visit will be discontinued from the study. However, patients who either complete the study or discontinue prematurely will be eligible for three months of free care at the clinic where they were enrolled. Patients who withdraw consent will no longer have data collected for the study. Every effort will be made to maintain contact with patients who are discontinued, but who do not withdraw consent, according to the study schedule (Table 3) for 30 days post-treatment in order to collect safety data.

I.5.b.2. PROTOCOL VIOLATION DEFINITIONS

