Protocol violations will be reported as described in the MOP.

J. TREATMENT

J.1. DOSING SCHEDULE

Ketamine 40 mg will be administered intranasally six times during the study. Ketamine will be administered at the respective visits, by study staff, onsite. Brexpiprazole or matching placebo will be administered orally daily for 28 days according to the fixed-flexible dose escalation schedule.

J.2. STUDY PRODUCT SUPPLIES AND ADMINISTRATION

Intranasal ketamine will be prepared as described in the Manual of Procedures. The intranasal ketamine will be supplied in a metered MAD Nasal™ Intranasal Mucosal Atomization Device. Each Intranasal Mucosal Atomization Device will contain 1mL of 40mg/mL Ketamine and be used for one administration. A total of two sprays, with one spray (a volume of 0.5 mL) given in each nostril, will be administered. A total of six atomization devices will be prepared for each patient.

Brexpiprazole and matching placebo, in .5 mg and 1 mg tablets, will be supplied to each site by Otsuka Pharmaceuticals. The site pharmacist will package the brexpiprazole and placebo tablets in bottles, and supply 4 bottles for each patient, according to the randomization scheme. Each bottle will contain 10, 20 or 30 pills, according to the dosage requirements listed below, of either brexpiprazole or placebo, and be labeled with the randomization number for that patient.

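### Contraception is required only during the study, with no period after the last brexpiprazole dose, although scheduled dosing ends at its highest level; add 30 days after the last dose

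*Combined protocol and SAP*

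**What the plan says.** **Contraception.** H.2.a criterion 7.b.iii requires women of childbearing potential to be "Willing and able to continuously use one of the following methods of birth control during the course of the study". H.2.b Exclusion 1 rules out a woman who is "not willing to use one of the specified forms of birth control during the study". The synopsis mentions birth control without a duration.

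**Dosing.** Under J.1, brexpiprazole or matching placebo "will be administered orally daily for 28 days". Table 6 and the text under Table 2 (I.1) step the dose from 0.5 mg to 1 mg at Day 8 and 2 mg at Day 14; then, "at Visit 9/Day 21, the dose will be increased to 3 mg/day". A patient who does not tolerate a step may return to the previous dose (I.1, J.4).

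**End of the study.** The last visit in Table 3 is Day 28, and I.1.c limits follow-up to 28 days after randomization. The synopsis and I.1.c also mention an end-of-study visit a week after the last double-blind visit. Table 3 has no such visit.

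**After the last dose.** I.4.d states: "Any pregnancy that occurs from Day 1 to 30 days following the last dose given will be followed for gestational outcome". I.4.b.1 collects unsolicited SAEs for 30 days after treatment. I.5.b.1 keeps contact with discontinued patients who have not withdrawn consent "for 30 days post-treatment in order to collect safety data". On testing, I.2.a says "the urine pregnancy and toxicity test will be performed at screen and baseline visits", and neither Table 3 nor Table 4 lists a later pregnancy test.

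**The concern.** A contraception rule should normally last as long as relevant exposure to the drug. Here it ends with the study, which on the visit schedule means at about the last dose. Because the dose is titrated upward, that is also when scheduled exposure is highest. A woman must use contraception from her first 0.5 mg tablet, yet the text asks nothing of her the day after her last 3 mg dose, when more drug than that is still in her body.

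The protocol shows awareness of carry-over elsewhere. For prohibited psychotropics, I.1.a requires that "the discontinuation of the excluded psychotropic medications occurs at least 5 half-lives prior to the baseline visit". It applies no comparable interval to its own study drug in the contraception rule. It also follows pregnancies occurring up to 30 days after the last dose, so it treats that month as relevant to pregnancy outcome while asking for no prevention in it. With no scheduled pregnancy test after baseline, a conception in that month would come to light only if reported.

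What is at stake is avoidable fetal exposure in a small number of participants. Power, type I error and the Day 14 SDQ comparison are unaffected. Ketamine plays no part in the argument: its last dose is on Day 21 and its half-life is given as 2.3 hours (D.2.a.2).

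**Working it through.** The plan states no figure for this interval, so there is none to reproduce. The check has two parts.

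**1. Days of cover under the stated rule**

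Cover = day the study ends − day of the last dose. The last dose is taken as Day 28. (If the 28 doses are counted from Day 0, the last falls on Day 27 and each cover figure rises by one day.)

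| Reading of the end of study | Cover after last dose | Days of the 30-day I.4.d window not covered |
|---|---|---|
| Day 28 (Table 3, I.1.c) | 28 − 28 = 0 | 30 − 0 = 30 |
| About Day 35 (synopsis wording) | 35 − 28 = 7 | 30 − 7 = 23 |

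**2. How long drug remains**

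Inputs from Table 6 and J.1: 28 daily doses on Days 0 to 27, made up of 0.5 mg × 8, 1 mg × 6, 2 mg × 7 and 3 mg × 7. *Assumption:* a one-compartment model with a half-life of 24 to 120 hours, because the documents give none. Bioavailability cancels in the ratios.

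- Load just after the last dose: L = Σ doseᵢ × 2^(−dᵢ/T), where dᵢ is days from dose i to the last dose and T is the half-life in days.
- Days until the load falls to that after the first dose (0.5 mg): T × log₂(L/0.5).
- Load left after k days: L × 2^(−k/T).

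Example, T = 1 day. The seven 3 mg doses give 3 × (1 − 2⁻⁷)/(1 − ½) = 5.95 mg. The seven 2 mg doses add 2⁻⁷ × 2 × (1 − 2⁻⁷)/(1 − ½) = 0.03 mg, and earlier doses add almost nothing. So L = 5.98 mg, which is 12.0 times 0.5 mg, and log₂(12.0) = 3.6 days.

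| Assumed half-life | Load after last dose | Multiple of first-dose load | Days above first-dose load | Five half-lives | Load left at 7 days |
|---|---|---|---|---|---|
| 24 h | 5.98 mg | 12.0 | 3.6 | 5 days | 0.05 mg |
| 48 h | 9.91 mg | 19.8 | 8.6 | 10 days | 0.88 mg |
| 72 h | 13.36 mg | 26.7 | 14.2 | 15 days | 2.65 mg |
| 96 h | 16.31 mg | 32.6 | 20.1 | 20 days | 4.85 mg |
| 120 h | 18.82 mg | 37.6 | 26.2 | 25 days | 7.13 mg |

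Zero days of cover meets neither measure at any half-life. Seven days is enough at 24 h and too short from 48 h upward. At 30 days the load left is at most 0.29 mg (the 120 h case), below the first-dose load, and five half-lives have passed throughout the range. Thirty days equals five half-lives at 144 h.

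**Sensitivity.** At a half-life of 12 h the excess over the first-dose load lasts only 1.5 days. For a patient who stays at 2 mg (0.5 mg × 8, 1 mg × 6, 2 mg × 14), the same model gives 3.0 to 24.0 days over 24 to 120 h, so stepping back does not remove the gap.

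**The case against.** **The half-life is not in the documents.** The results run from 3.6 to 26.2 days, nothing in the protocol favours the upper end, and at 24 h a 7-day tail would be enough. This stands as a limit on the calculation: it cannot by itself produce 30 days. That figure rests mainly on the 30-day windows the protocol already uses.

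**The 0.5 mg benchmark is not a safety threshold.** Contraception is an entry condition that applies equally to placebo patients. It does not say that 0.5 mg is a level of concern. The brexpiprazole data shown find no genotoxic risk to humans (D.1.b.2) and reduced fertility in female rats at 7.3 and 73 times the maximum recommended human dose (D.1.b.3). This also stands. The benchmark only compares exposure the rule covers with exposure it leaves uncovered, and no harm at residual levels is claimed.

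**The five-half-life rule serves another purpose.** It clears excluded drugs before baseline and is not a reproductive-safety standard. So its absence from the contraception criteria is not a contradiction. It shows only how the protocol treats clearance elsewhere.

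**The end of the study is open to interpretation.** Safety contact and SAE reporting run past Day 28, so zero days is one reading. But those provisions are reporting rules and require no contraception. The ambiguity is itself a reason to state an end date.

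**Consent pages were not available.** An instruction could sit there. Even so, the two eligibility criteria would need to agree with it.

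**Completers have no scheduled contact after Day 28,** so compliance in the added month could not be checked for them. This is true, and it limits the rule to an agreed commitment.

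**Conclusion.** The concern holds. As written, the two criteria require about zero days of contraception after the last dose, or about 7 on the most generous visit-based reading. That leaves 30 or 23 days of the protocol's own pregnancy follow-up window without any preventive requirement. The I.4.d rule is surveillance; it neither fills the gap nor contradicts the contraception criteria.

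That the precaution lapses while some drug remains follows for any plausible half-life under the Day 28 reading. How long the gap lasts depends on the assumed 24 to 120 h range and, for the main table, on full titration to 3 mg. The choice of 30 days is best supported by alignment with I.4.d and I.4.b.1. It also covers the whole assumed range.

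This is an optional improvement to safety wording, held with medium confidence. It has no bearing on sample size, power, error control or the efficacy analysis.

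**What to change.** - **H.2.a, 7.b.iii:** require contraception *during the course of the study and for 30 days after the last dose of study drug (brexpiprazole/placebo), including after early termination*.
- **H.2.b, Exclusion 1:** change the ending to *during the study and for 30 days after the last dose of study drug*.
- **Consent form:** use the same wording if it is not already there.
- **I.4.d:** keep the pregnancy follow-up window at 30 days or longer.

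With the last dose at Day 28, contraception would run to about Day 28 + 30 = Day 58, the same end as the I.4.d window.

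The cost is wording in two criteria, plus consent text if needed, with no added visits or tests. The downside is about one more month of contraception for women of childbearing potential, which may be longer than necessary if the half-life is short.

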#### H.2.b. EXCLUSION CRITERIA

A potential participant will NOT be eligible for participation in this study if any of the following criteria are met:

1. Female of childbearing potential who is not willing to use one of the specified forms of birth control during the study.
2. Female that is pregnant or breastfeeding.
3. Female with a positive pregnancy test at screening or baseline.
4. History during the *current* MDE of failure to achieve satisfactory response (e.g., less than 50% improvement of depression symptoms) to >7 treatment courses of a therapeutic dose of an antidepressant therapy of at least 8 weeks duration, according to the MGH ATRQ, as confirmed by the remote, independent MGH CTNI rater.
5. Total MADRS score of <20 at the screen visit or the baseline visit, or as assessed by the remote, independent MGH CTNI rater and reported to the site.
6. Current diagnosis of a substance use disorder (abuse or dependence, as defined by DSM V-TR™), with the exception of nicotine dependence, at screening or within 6 months prior to screening.
7. Current Axis I disorder, diagnosed at screening with the use of the Structured Clinical Interview for DSM-5 AXIS I Disorders (SCID-5), that is the principal focus of treatment and MDD the secondary focus of treatment for the past 6 months or more.
8. History of bipolar disorder, schizophrenia or schizoaffective disorders, or any history of psychotic symptoms in the current or previous depressive episodes.
9. History of anorexia nervosa, bulimia nervosa, or eating disorder not otherwise specified, within 5 years of screening.
10. Any Axis I or Axis II Disorder, which at screening is clinically predominant to their MDD or has been predominant to their MDD at any time within 6 months prior to screening.
11. In the judgment of the investigator, the subject is considered at significant risk for suicidal behavior during the course of his/her participation in the study.
12. Has failed to respond to ECT during the current depressive episode.
13. Has received VNS at any time prior to screening.
14. Has dementia, delirium, amnestic, or any other cognitive disorder.
15. Has a clinically significant abnormality on the screening physical examination that might affect safety, study participation, or confound interpretation of study results according to the study clinician.
16. Participation in any clinical trial with an investigational drug or device within the past month or concurrent to study participation.
17. Current episode of:
  - a. Hypertension, Stage 1 as defined by a systolic blood pressure  $\geq 160$  mmHg or diastolic blood pressure  $\geq 100$  mmHg at the Screening and Baseline Visits within 1.5

- hours prior to randomization on two of three measurements (standing and supine) at least 15 minutes apart.
- b. Recent myocardial infarction (within one year) or a history of myocardial infarction.
  - c. Syncope event within the past year.
  - d. Congestive heart failure (CHF) New York Heart Association Criteria >Stage 2
  - e. Angina pectoris.
  - f. Heart rate <45 or >110 beats per minute at screening or randomization (Baseline Visit).
  - g. QTcF (Fridericia-corrected)  $\geq 450$  msec at screening or randomization (Baseline Visit).
18. Chronic lung disease excluding asthma.
19. Lifetime history of surgical procedures involving the brain or meninges, encephalitis, meningitis, degenerative central nervous system (CNS) disorder (e.g., Alzheimer's or Parkinson's Disease), epilepsy, mental retardation, or any other disease/procedure/accident/intervention which, according to the screening clinician, is deemed associated with significant injury to or malfunction of the CNS, or history of significant head trauma within the past 2 years.
20. Presents with any of the following lab abnormalities:
- a. Thyroid stimulating hormone (TSH) outside of the normal limits and clinically significant as determined by the investigator. Free thyroxine (T4) levels may be measured if TSH level is high. Subject will be excluded if T4 level is clinically significant.
  - b. Patients with diabetes mellitus fulfilling any of the following criteria:
    - i. Unstable diabetes mellitus defined as glycosylated hemoglobin (HbA1c) >8.5% at screening.
    - ii. Admitted to hospital for treatment of diabetes mellitus or diabetes mellitus-related illness in the past 12 weeks.
    - iii. Not under physician care for diabetes mellitus.
    - iv. Has not been on the same dose of oral hypoglycaemic drug(s) and/or diet for the 4 weeks prior to screening. For thiazolidinediones (glitazones) this period should not be less than 8 weeks.
  - c. Any other clinically significant abnormal laboratory result (determined as such by the investigator and MGH CTNI medical monitor) at the time of the screening.
21. History of hypothyroidism and has been on a stable dosage of thyroid replacement medication for less than 2 months prior to screening. (Subjects on a stable dosage of thyroid replacement medication for at least 3 months or more prior to screening are eligible for enrollment.)

22. History of hyperthyroidism which was treated (medically or surgically) less than 6 months prior to screening.
23. History of positive screening urine test for drugs of abuse at screening: cannabinoids (if the patient has a legitimate medical prescription for cannabis, patient must agree to abstain during the entirety of the study and to have a negative test at baseline), cocaine, amphetamines, barbiturates, opiates (unless use is in accordance with guidance provided in table of allowed and excluded medications).
24. Patients with exclusionary laboratory values (see Table 1), or requiring treatment with exclusionary concomitant medications (see Appendix 1).
25. Patients on exclusionary concomitant psychotropic medications, the half-life of which would not allow sufficient time for patients to have been free of the medication post-taper for five half-lives within the maximum screening period (28 days).
26. Patients with a history of narrow angle glaucoma.
27. Liver or renal Function tests which meet the exclusion criteria in Table 1, or a history of hepatic or renal dysfunction.

